### 5.3.3. Handling of Incomplete or Missing Dates

#### 5.3.3.1. Adverse Events

**AE Onset Date:** If the AE onset date is completely missing, and if the date of first dose is less than AE stop date, then the onset date will be assigned as the date of first dose. Otherwise if the date of first dose is after the AE stop date then the AE onset date will be imputed as the earliest of non-missing AE stop date or informed consent date.

**AE Stop Date:** If the AE stop date is completely missing then the stop date will be imputed as the latest of the participant withdrawal/completion date, death date, last dose of study intervention, or AE onset date.

#### 5.3.3.2. Exposure

No imputation will be done for first dose date. Date of last dose of study intervention, if unknown or partially unknown, will be imputed as follows:

- If the last date of study intervention is completely missing and there is no End of Treatment (EOT) CRF page and no death date, the participant should be considered to be ongoing and use the data cutoff date for the analysis as the last dosing date; or

- If the last date of study intervention is completely or partially missing and there is either a PF-06863135 EOT CRF page or a death date available (on or prior to the data cutoff date), then impute this date as the last dose date:
  - = 31DECYYYY, if only Year is available and Year < Year of min (EOT date, death date),
  - = Last day of the month, if both Year and Month are available and Year = Year of min (EOT date, death date) and Month < the month of min (EOT date, death date), or
  - = min (EOT date, death date), for all other cases.

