MMM < Month of min [max(PD date + 1 day, last dose of study intervention + 1 day), end date of new anticancer therapy];

THEN imputed start date = DAY (Last day of MMM) MMM YYYY;
    - ELSE IF YYYY = Year of min [max(PD date + 1, last dose of study intervention + 1), end date of new anticancer therapy], AND
 

MMM = Month of min [max(PD date + 1 day, last dose of study intervention + 1 day), end date of new anticancer therapy];

THEN imputed start date = min [max(PD date + 1 day, last dose of study intervention + 1 day), end date of new anticancer therapy];
    - ELSE IF YYYY = Year of min [max(PD date + 1, last dose of study intervention + 1), end date of new anticancer therapy], AND
 

MMM > Month of min [max(PD date + 1 day, last dose of study intervention + 1 day), end date of new anticancer therapy];

090177e196913362\Approved\Approved On: 19-Mar-2021 12:41 (GMT)

THEN imputed start date = 01 MMM YYYY;

- ELSE IF YYYY < Year of min [max(PD date + 1, last dose of study intervention + 1), end date of new anticancer therapy]

THEN imputed start date = DAY (Last day of MMM) MMM YYYY;

- ELSE IF YYYY > Year of min [max(PD date + 1, last dose of study intervention + 1), end date of new anticancer therapy]

THEN imputed start date = 01 MMM YYYY.

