### 5.3.3.5. Other Dates

Imputation methods for other partial dates are as follows:

- If the day of the month is missing for a start date used in a calculation, the first day of the month will be used to replace the missing date;
- If both the day and month are missing, the first day of the year is used;
- For stop dates, the last day of the month, or last day of the year is used if the day or day and month are missing, respectively;
- If the date is completely missing, no imputation will be performed.

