**Table 2. Study Intervention Dose Levels and Administration**

Dose Levels (DL)	Elranatamab	Nirogacestat
1 (starting dose level)	Priming Dose: 4 mg C0D1 SC Full Dose: 4 mg C1D1 SC, weekly thereafter b	100 mg PO BID continuous starting on C1D1 until response a
2	2 Step-up Priming Dose: 4 mg C0D1 SC / 8 mg C0D4 SC Full Dose: 12 mg C1D1 SC, weekly thereafter b	100 mg PO BID continuous starting on C1D1 until response a
3	2 Step-up Priming Dose: 12 mg C0D1 SC / 32 mg C0D4 SC Full Dose: 32 mg C1D1 SC, weekly thereafter b	100 mg PO BID continuous starting on C1D1 until response a
Nirogacestat De-Escalation Levels		
3A	2 Step-up Priming Dose: 12 mg C0D1 SC / 32 mg C0D4 SC Full Dose: 32 mg C1D1 SC, weekly thereafter b	100 mg PO QD continuous starting on C1D1 until response a
4A	2 Step-up Priming Dose: 12 mg C0D1 SC / 32 mg C0D4 SC Full Dose: 76 mg C1D1 SC, weekly thereafter b,c	100 mg PO QD continuous starting on C1D1 until response a
3B	2 Step-up Priming Dose: 12 mg C0D1 SC / 32 mg C0D4 SC Full Dose: 32 mg C1D1 SC, weekly thereafter b	50 mg PO QD continuous starting on C1D1 until response a
4B	2 Step-up Priming Dose: 12 mg C0D1 SC / 32 mg C0D4 SC Full Dose: 76 mg C1D1 SC, weekly thereafter b,c	50 mg PO QD continuous starting on C1D1 until response a

- a. For Dose levels 3A/3B and 4A/4B, nirogacestat will be adjusted to 50 mg QD continuous at time of confirmed VGPR. Once CR (or better) is confirmed, nirogacestat will be permanently discontinued. For all other dose levels, nirogacestat can be continued or adjusted based on this guidance, per investigator discretion. See Section 6.1.1.5.
- b. Starting at Cycle 7, if a participant has received QW dosing for at least 6 cycles and PR or better persisting for ≥2 months, dose interval will be changed from QW to Q2W. See Schedule of Activities.
- c. For participants on Dose levels 4A and 4B receiving CCI dosing, CCI the dose interval will be changed to CCI

090177e1a0f4f44c\Approved\Approved On: 14-Jun-2024 22:12 (GMT)

CCI

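### The last-dose imputation rule has no branch for a recorded month in an earlier calendar year, so it overwrites that month with a date that is always too late

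*SAP*

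**What the plan says.** The SAP dated 18 March 2021 is taken here as the master SAP that the sub-study A and B SAPs cite. Its Section 5.3.3.2 deals with an incomplete last-dose date. The relevant part opens "If the last date of study intervention is completely or partially missing and there is either a PF-06863135 EOT CRF page or a death date", on or before the data cutoff. Below, *anchor* means the earlier of the EOT date and the death date. Three branches follow.

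1. Year only recorded: "31DECYYYY, if only Year is available and Year < Year of min (EOT date, death date").
2. Month and year recorded: "Last day of the month, if both Year and Month are available and Year = Year of min (EOT date, death date"), and the recorded month is before the anchor's month.
3. Default: "min (EOT date, death date), for all other cases".

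Two neighbouring rules matter for comparison.

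- Section 5.3.3.4 (start of new anticancer therapy, month and year recorded) has a separate branch for an earlier year, "ELSE IF YYYY < Year of min [max(PD date + 1, last dose of study intervention + 1), end date of new anticancer therapy"]. It returns the last day of the recorded month.
- Section 5.3.3.5 covers other dates: "For stop dates, the last day of the month, or last day of the year is used" when the day, or the day and month, are missing. It does not govern last dose, which has its own rule.

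Neither sub-study SAP contains a replacement rule for the last-dose date.

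**The concern.** Branch 1 does not apply when the month is also recorded. Branch 2 requires the recorded year to equal the anchor's year. A month-year record from an earlier year therefore drops to branch 3, and the imputed date contradicts the month that the site entered. The error runs in one direction only, because the anchor is then later than every day of the recorded month.

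The last-dose date feeds several results:

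- the on-treatment period, which closes 28 days after last dose or the day before new anticancer therapy, whichever is earlier (Section 3.5);
- treatment-emergent status of adverse events (Section 3.5.1);
- the table of deaths within 28 days of last dose (Section 6.7.2);
- treatment duration (Section 6.6.3, and Section 6.6.3.1 in both sub-study SAPs);
- the term for the day after last dose in Section 5.3.3.4, which helps to set censoring dates when the start of new therapy is itself incomplete.

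**Working it through.** The plan states no figure to reproduce. The check applies the three branches literally and compares them with the logic of Section 5.3.3.4.

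**Step 1. Cases.** The last column is the imputed date minus the last day of the recorded month.

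| Recorded last dose | Anchor | Branch | Imputed | Days past recorded month |
|---|---|---|---|---|
| OCT2022 | 20 Dec 2022 | 2 | 31 Oct 2022 | 0 |
| 2022 only | 20 Jan 2023 | 1 | 31 Dec 2022 | n/a |
| DEC2022 | 20 Jan 2023 | 3 | 20 Jan 2023 | 20 |
| NOV2022 | 20 Jan 2023 | 3 | 20 Jan 2023 | 51 |
| OCT2022 | 10 Feb 2023 | 3 | 10 Feb 2023 | 102 |
| SEP2022 | 15 Mar 2023 | 3 | 15 Mar 2023 | 166 |

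The same-year case works. Rows 2 and 4 show that more information gives a worse answer: with the same anchor, the bare year yields 31 December and the recorded November yields 20 January.

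**Step 2. A death example.** Last dose is DEC2022, death is on 10 February 2023, and there is no EOT page. Assume that the partner drug also stopped by 31 December 2022 and that no new therapy started.

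- Imputed last dose: 10 February 2023, the day of death.
- Latest date compatible with the record: 31 December 2022. From there to death is 31 + 10 = 41 days. From 1 December it is 30 + 41 = 71 days. The true interval is therefore 41 to 71 days, always more than 28.
- The rule gives 0 days, so the death is certainly misclassified as within 28 days of last dose.
- The on-treatment period should close no later than 31 December + 28 days = 28 January 2023. Events starting 29 January to 10 February are wrongly treatment-emergent.
- Under the sub-study formula for elranatamab duration (last minus first dose date, plus 1, divided by 7), the result is at least 41/7 = 5.9 weeks too long.

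**Step 3. How often.** The documents do not give the gap from true last dose to anchor, so it is varied. Last-dose days are spread evenly over a 365-day year. With a gap of k days (k below 365), the last k days of the year cross into the next one, so the share affected is k/365. The excess is measured against the last day of the recorded month.

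| Assumed gap (days) | Share of month-year partial dates affected | Mean excess (days) |
|---|---|---|
| 14 | 14/365 = 3.8% | 7.5 |
| 28 | 28/365 = 7.7% | 14.5 |
| 35 | 35/365 = 9.6% | 21.5 |
| 60 | 60/365 = 16.4% | 45.5 |
| 90 | 90/365 = 24.7% | 75.5 |
| 180 | 180/365 = 49.3% | 165.5 |

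The denominator is last-dose dates with month and year but no day. It is not all participants.

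**Step 4. Partner drug.** The only EOT page that the rule names is the elranatamab one. Sub-study A SAP Table 2, footnote a, says for dose levels 3A/3B and 4A/4B: "Once CR (or better) is confirmed, nirogacestat will be permanently discontinued". Nirogacestat can therefore end long before elranatamab. If the rule is applied to nirogacestat's own last dose, recorded NOV2023, with an elranatamab EOT date of 15 October 2024, the imputed date is 320 days past 30 November 2023.

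**The case against.** **Which document governs.** The sub-study SAPs cite master SAP sections for baseline, disposition and safety summaries (6.5.1, 6.5.2, 6.6) that are numbered 6.6.1, 6.6.2 and 6.7 in the March 2021 text. A different master SAP might exist. This inference rests on shifted numbers alone. Other cross-references (3.4, 4, 5.2.6, 5.3.1) match, and no other last-dose rule appears in the documents.

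**Rarity.** Elranatamab is given at the site by trained staff (Protocol 6.1.1), and the time of each injection goes into the CRF (Protocol Appendix 10). A missing day should be uncommon, and the date must also cross a year end. This stands and limits the reach.

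**Trigger.** A reader might infer that any EOT or death date in a later year sets off the problem. It does not. The earlier of the two must fall in a later year. If EOT is in the recorded year and only the death is later, the anchor is the EOT date and the recorded month is not lost in this way.

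**The nirogacestat example.** A reader might infer that the 320 days shift the safety window. They do not. Section 3.4 takes the latest last dose across the drugs in the combination, so the on-treatment period and the death table follow elranatamab. The 320 days reach only nirogacestat treatment duration. The stop at confirmed CR is also mandatory only at 3A/3B and 4A/4B; at other levels it is left to the investigator.

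**Dose intensity.** A reader might also infer that dose intensity is distorted. Both sub-study SAPs compute it from an intended treatment duration keyed to the last zero or non-zero dose date, so the documents do not support that.

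**Conclusion.** The rule is wrong as written. For a recorded month in a year before the anchor's, it returns a date that the record rules out, and always a late one. The handling of year-only dates in the same section, and the explicit earlier-year branch in Section 5.3.3.4, point to an omission and not a deliberate convention.

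The consequences in an affected case are definite, as the death example shows. They fall on safety windows and exposure duration. Responder counts for ORR are not directly touched, and an effect on censoring needs a second incomplete date. The number affected is probably small. The range of about 4% to 49% of month-year partial dates rests on assumed gaps of 14 to 180 days and evenly spread last doses. No single value in it, such as 16% at 60 days, should be read as an estimate for this trial. The correction should be made because it removes a certain error at almost no cost, not because it is likely to change a conclusion.

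**What to change.** Restate branch 2 of Section 5.3.3.2: if month and year are both recorded and that month-year is earlier than the month-year of the anchor, impute the last day of the recorded month. This matches Section 5.3.3.4. In Step 1 the affected dates become 31 December, 30 November, 31 October and 30 September 2022. In Step 2 last dose becomes 31 December 2022, and the death leaves the 28-day table. Same-year results do not change.

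Secondary: where the rule is applied to a combination partner's own last dose, name that drug's own discontinuation date as the anchor in place of the elranatamab EOT page. Section 6.6.2.1 already reports discontinuation of the partner separately, so such a date appears to be collected. The first change alone would resolve the November 2023 example. The second still matters when the partner's last-dose date is wholly missing, or has only a year equal to the anchor's year.

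The cost is two lines in the SAP and the matching edits in the derivation program, with no new data collection. While the section is open, add a line for a partial date with neither an EOT page nor a death date, which fits neither bullet at present.

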### 5.3.3.3. Date of Death

Missing or partial death dates will be imputed based on the last contact date:

- If the date is missing, it will be imputed as the day after the date of last contact;
- If the day or both day and month is missing, death will be imputed to the maximum of the full (non-imputed) day after the date of last contact and the following:
  - Missing day: 1st day of the month and year of death;
  - Missing day and month: January 1st of the year of death.

### 5.3.3.4. Date of Start of New Anticancer Therapy

Incomplete dates for start date of new anticancer therapy (drug therapy, radiation with curative intent) will be imputed as follows and will be used for determining censoring dates for efficacy analyses and in the derivation of the end of the on-treatment period. PD date below refers to PD date by investigator assessment. If the imputation results in an end date prior to the imputed start date, then the imputed start date should be set to the end date.

- The end date of new anticancer therapy will be included in the imputations for start date of new anticancer therapy. If the end date of new anticancer therapy is
  - completely missing then it will be ignored in the imputations below;
  - partially missing with only year (YYYY) available then the imputations below will consider 31DECYYYY as the end date of the new anticancer therapy;
  - partially missing with only month and year available then the imputations below will consider the last day of the month for MMMYYYY as the end date of the new anticancer therapy.
- For participants who have not discontinued study intervention at the analysis cutoff date, last dose of study intervention is set to the analysis cutoff date in the imputations below.

- If the start date of new anticancer therapy is completely or partially missing, then the imputed start date of new anticancer therapy is derived as follows:
  - Start date of new anticancer therapy is completely missing
    - Imputed start date = min [max(PD date + 1, last dose of study intervention + 1), end date of new anticancer therapy]
  - Only year (YYYY) for start of anticancer therapy is available
    - IF YYYY < Year of min [max(PD date + 1, last dose of study intervention + 1), end date of new anticancer therapy]
 

THEN imputed start date = 31DECYYYY;
    - ELSE IF YYYY = Year of min [max(PD date + 1, last dose of study intervention + 1), end date of new anticancer therapy]
 

THEN imputed start date = min [max(PD date + 1, last dose of study intervention + 1), end date of new anticancer therapy];
    - ELSE IF YYYY > Year of min [max(PD date + 1, last dose of study intervention + 1), end date of new anticancer therapy]
 

THEN imputed start date = 01JANYYYYY.
  - Both Year (YYYY) and Month (MMM) for start of anticancer therapy are available
    - IF YYYY = Year of min [max(PD date + 1, last dose of study intervention + 1), end date of new anticancer therapy], AND
 

MMM < Month of min [max(PD date + 1 day, last dose of study intervention + 1 day), end date of new anticancer therapy];

THEN imputed start date = DAY (Last day of MMM) MMM YYYY;
    - ELSE IF YYYY = Year of min [max(PD date + 1, last dose of study intervention + 1), end date of new anticancer therapy], AND
 

MMM = Month of min [max(PD date + 1 day, last dose of study intervention + 1 day), end date of new anticancer therapy];

THEN imputed start date = min [max(PD date + 1 day, last dose of study intervention + 1 day), end date of new anticancer therapy];
    - ELSE IF YYYY = Year of min [max(PD date + 1, last dose of study intervention + 1), end date of new anticancer therapy], AND
 

MMM > Month of min [max(PD date + 1 day, last dose of study intervention + 1 day), end date of new anticancer therapy];

090177e196913362\Approved\Approved On: 19-Mar-2021 12:41 (GMT)

THEN imputed start date = 01 MMM YYYY;

- ELSE IF YYYY < Year of min [max(PD date + 1, last dose of study intervention + 1), end date of new anticancer therapy]

THEN imputed start date = DAY (Last day of MMM) MMM YYYY;

- ELSE IF YYYY > Year of min [max(PD date + 1, last dose of study intervention + 1), end date of new anticancer therapy]

THEN imputed start date = 01 MMM YYYY.

### 5.3.3.5. Other Dates

Imputation methods for other partial dates are as follows:

- If the day of the month is missing for a start date used in a calculation, the first day of the month will be used to replace the missing date;
- If both the day and month are missing, the first day of the year is used;
- For stop dates, the last day of the month, or last day of the year is used if the day or day and month are missing, respectively;
- If the date is completely missing, no imputation will be performed.

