#### 3.5.1. Adverse Events

An adverse event is considered treatment-emergent relative to the study intervention if the event start date is during the on-treatment period (including on the date of first dose).

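### Partial AE onset dates have no rule of their own; under the general first-of-month rule, an on-treatment event in the calendar month of first dose can drop out of the TEAE summaries

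*SAP*

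**What the plan says.** Four parts of the master SAP (version 1, 18 March 2021) combine here.

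- **Onset completely missing (5.3.3.1).** The AE section opens its onset rule with "If the AE onset date is completely missing, and if the date of first dose is less than AE stop date", and in that case "then the onset date will be assigned as the date of first dose". The event therefore counts as treatment-emergent. The section says nothing about an onset date that is only partly known.
- **Remaining partial dates (5.3.3.5).** This section is introduced by "Imputation methods for other partial dates are as follows". For a start date with no day, "the first day of the month will be used to replace the missing date". When the month is absent as well, "If both the day and month are missing, the first day of the year is used". There is no comparison with first dose or with the stop date.
- **Treatment-emergent status (3.5 and 3.5.1).** An AE qualifies "if the event start date is during the on-treatment period", and that period begins at first dose.
- **Reporting (6.7.1).** AE analyses use TEAEs unless otherwise specified. Other AEs are flagged in listings.

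The Sub-study A and Sub-study B SAPs refer to the master SAP for safety endpoint definitions (their Section 3.5). Neither adds a date rule for AEs.

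**The concern.** The two rules run in the wrong order: a site that records the month of onset can cause an event to be excluded that would have been included had it recorded no date at all. Nothing in the plan explains this.

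It also sits badly with the plan's other conventions. Partial death dates have a floor at the day after last contact (5.3.3.3). Partial start dates of new anticancer therapy are compared by month and year with a reference date (5.3.3.4). AEs on the day of first dose count as on-treatment (3.5), and a missing causality assessment counts as related (6.7.1). The partial AE onset date is the exception, and at the first-dose boundary it leans toward under-counting.

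AEs are the primary endpoint of the Sub-study B dose expansion (Sub-study B SAP 3.1.2), with up to 20 participants, so one participant lost from a TEAE row is 1/20 = 5 percentage points. In Sub-study A, AEs are a secondary endpoint in both phases.

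**Working it through.** The plan gives no figure on this point, so there is none to reproduce. The check applies its rules to dates.

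**Worked example.** First dose 15 June 2022, true onset 17 June, stop date 20 June.

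| What the site records for onset | Rule | Imputed onset | TEAE? |
|---|---|---|---|
| Nothing | 5.3.3.1 | 15 June 2022 | Yes |
| June 2022, day missing | 5.3.3.5 | 1 June 2022 | No |
| 2022 only | 5.3.3.5 | 1 January 2022 | No |

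**Probability of loss, day missing.** Inputs: the first-of-month rule (5.3.3.5) and the TEAE definition (3.5, 3.5.1). Assumption: first-dose day d is uniform over 1 to 30 in a 30-day month. An event with true onset on study day s falls on calendar day d + s − 1. It is lost when

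- the onset is in the same month as first dose: d + s − 1 ≤ 30, and
- dosing did not start on the 1st: d > 1.

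The qualifying d run from 2 to 31 − s, so the probability is (30 − s)/30.

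| True study day s | (30 − s)/30 | Probability |
|---|---|---|
| 1 | 29/30 | 0.97 |
| 3 | 27/30 | 0.90 |
| 8 | 22/30 | 0.73 |
| 15 | 15/30 | 0.50 |

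**Check on real calendar months.** With first-dose dates spread evenly over 2021 to 2023 (1,095 days, an assumption), the shares are 96.7% on day 1, 90.1% on day 3, 73.7% on day 8 and 50.7% on day 15. Over all pairs of first-dose date and same-month onset on or after it, 16,119 of 17,214 (93.6%) become non-TEAE. The exceptions are the 1,095 pairs in which dosing began on the 1st: 17,214 − 1,095 = 16,119.

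**Day and month both missing.** On the same calendar, the loss is 99.7% for a true onset on day 1 (only a first dose on 1 January escapes: 1,092/1,095) and 95.9% on day 15.

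Every figure is conditional on two things: the onset date is partial, and the event was truly on-treatment. The documents do not say how often onset dates are partial.

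**With a floor at first dose.** If a same-month or same-year onset is set to the first dose date unless the AE stopped earlier, the share of truly on-treatment events lost in this way falls to zero.

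**The case against.** Several objections have force.

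- **5.3.3.5 does not name AEs.** True. That partial onsets go there is the natural reading, since AEs have their own subsection and it is silent on them, but the SAP does not state it. If 5.3.3.5 was not meant to apply, partial AE onsets have no rule at all, and the same sentences are needed.
- **The error does not always run one way.** A reader might infer that first-of-month imputation only removes TEAEs. The documents do not support that. The on-treatment period ends at most 28 days after last dose (3.5), while AEs are collected for at least 90 days (Protocol 8.3.1). With last dose on 10 March the period ends on 7 April. A true onset of 20 April, recorded only as April, becomes 1 April and enters the TEAE set. The under-count is specific to the first-dose boundary.
- **CRS and ICANS are poor examples.** A reader might infer that early CRS or ICANS would go missing. Both have dedicated forms, with symptom timing summarized in hours or days (master SAP 6.7.1.1), and vital signs are taken every 4 hours during hospitalization for study intervention (Protocol 8.2.2). A missing onset day is unlikely for them.
- **No decision rule is shown to move.** A reader might infer that DLT counts or enrollment holds are at risk. DLT rates and hold thresholds have their own evaluability definitions and do not refer to TEAE status. The Sub-study B expansion has no hypothesis and no decision rule.
- **The operative master SAP may differ.** The one provided is based on Amendment 1, under which no participant could enroll, and lists only Sub-study A. The sub-study SAPs cite baseline summaries at master 6.5.1 and safety at 6.6; here they are at 6.6.1 and 6.7. Other cross-references (3.4, 3.5, 4, 5.2, 5.3.1) do match. A restructured version is possible, so the link to Sub-study B is less certain than the defect in the text itself.
- **Some same-month events really are pre-treatment.** AEs are collected from consent, so the proposed rule will misclassify a few in the other direction.

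These points limit the reach of the concern. They do not explain why a partly known date should be treated less conservatively than an unknown one.

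**Conclusion.** The defect is real and narrow. As written, and reading 5.3.3.5 as the rule for partial AE onsets, an on-treatment AE is dated before first dose whenever its known month (or year alone) equals that of first dose and dosing did not begin on the first day of that period. It leaves the TEAE summaries and stays flagged in listings.

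For a missing day the loss probability is about 0.97, 0.73 and 0.50 for true onsets on study days 1, 8 and 15, assuming a uniform first-dose day in a 30-day month. The absolute effect depends on the number of partial onset dates, which is unknown and probably small. A lost event also changes a count only when the participant has no other TEAE of the same preferred term.

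The documents support under-counting at the first-dose boundary and an inconsistency with the rule for fully missing dates. They do not support a one-directional bias overall, an effect on DLT or hold rules, or a particular loss of CRS and ICANS events. The change is worth making because it is specific and nearly free.

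**What to change.** Add a partial-date rule to master SAP 5.3.3.1:

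- If the known onset month and year, or the year alone when the month is missing, equal those of first dose, set the onset to the first dose date unless the AE stop date is before first dose.
- Otherwise use the first day of the known month, or of the known year.

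Carry the rule into whichever master SAP version Sub-studies A and B use, and check the section references at the same time.

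The cost is two sentences and a small change to the AE derivation, with no new data collection. The downside is that a few truly pre-treatment events that continue past first dose, or have no stop date, will be counted as TEAEs. That is the conservative direction and in line with how the plan already treats a fully missing onset date.
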